8.0 CRITERIA FOR REMOVAL FROM PROTOCOL THERAPY AND OFF STUDY CRITERIA

8.1 Criteria for Removal from Protocol Therapy

- a. Completion of therapy.
- b. Patient develops a *LBP*-associated bacteremia.
- c. Patient relapses.
- d. Patient develops another malignancy.
- e. Refusal of further protocol therapy by patient/parent/guardian.
- f. Physician determines it is in patient's best interest.
- g. Patient requires emergency unblinding.
- h. Patient never received transplant.
- i. Patient experiences an adverse event requiring removal from protocol therapy.
- j. Repeat eligibility studies (if required) or change in patient condition(s) prior to the initiation of protocol therapy are outside the parameters required for eligibility (see [Section 3.2](#) and [Section 3.3](#)).
- k. Patient develops graft failure (see [Section 10.3](#)).

Patients who are off protocol therapy are to be followed until they meet the criteria for Off Study (see below). Follow-up data will be required unless patient is taken off study. Follow up time is defined as the duration of time between patient enrollment and assessment of primary outcome (120 days after enrollment).

8.2 Off Study Criteria

- a. Death.
- b. Lost to follow-up.
- c. Withdrawal of consent for any further data submission.
- d. Patient never received conditioning
- e. Completion of follow-up through Day 120.

9.0 STATISTICAL CONSIDERATIONS

9.1 Sample Size and Study Duration

Based on estimates from Center of International Blood and Marrow Transplant Research (CIBMTR), approximately 1,400 allogeneic SCTs are performed at COG institutions each year with approximately 25% of them (350 per year) meeting the definition of "alternative donor" as defined in this study. If 30% of those eligible are enrolled, the accrual rate will be about 105 per year. Accounting for start-up time and possible delay of up to 4 months between the two stages of the study, we project accrual to the screening stage within 1.2 years and total accrual duration of 5 years. The sample size of 454 (the first 120 for the screening stage and an additional 334 for the confirmatory stage) may be increased to a maximum of 500 patients (up to 132 for screening stage and an additional 368 for the confirmatory stage) to conservatively account for up to 10% loss due to ineligible or not being randomized to a treatment regimen. Evaluable patients are defined as eligible (or meeting repeated eligibility criteria) randomized patients.

9.2 Study Design

This is a randomized, double-blind intervention trial evaluating the efficacy of *LBP* in preventing GI aGvHD in children and adolescents undergoing alternative donor HCT.

Patients will be randomized to receive daily *LBP* or placebo using a 1:1 allocation. Randomization will be stratified by stem cell source (cord vs. marrow or PBSC), HLA degree of match (complete match vs. 1 mismatch vs. 2 or more mismatches), and GvHD prophylaxis (ATG/CAMPATH vs. No ATG/CAMPATH). Haplo patients are those who have a related donor with 2 or more HLA mismatches. For stratification, Haplo would be included into the stem cell source. AGvHD outcomes will be assessed from day of stem cell infusion (Day 0) through Day 120. Accrual will be conducted in two stages: a randomized *screening* stage, and a larger *confirmatory* stage. The screening stage will compare the rate of GI aGvHD between the 2 arms at $\alpha=0.30$ (1-sided). After recruitment of 120 patients (up to a maximum of 132 to account for up to 10% loss due to patients deemed to be ineligible or not being randomized to a treatment regimen), the evaluation of the outcome will be assessed. If the screening stage suggests efficacy ($p<0.3$), the study will proceed to the confirmatory stage (N=454). We will use a modified intention-to-treat analytic approach for all evaluable patients. Based on previous CCL studies, we expect the inevaluable rate to be very low.

The primary outcome measure is the incidence of Stage 1-4 GI aGvHD from the day of stem cell infusion (Day 0) through Day 120.

Endpoint incidence is assumed for evaluable patients who are lost to follow up including withdrawal of further data submission and death prior to determination of their outcome (stage 1-4 of GI aGvHD and grade II-IV overall GvHD) in the primary analysis.

Patients who never received conditioning are not at risk of aGvHD and will be considered invaluable for the primary outcome analysis. Patients who have graft failure are not at risk for graft versus host disease, therefore, they will contribute to the primary analysis up to date of graft failure. However, they can still be included in the analysis of toxicity data and laboratory data. See [Section 10.3](#) for definition of graft failure.

Exploratory endpoints include the incidence of Grade II–IV overall aGvHD, blood stream infection (BSI), *Clostridium difficile*-associated diarrhea and assessment of laboratory correlative measures for serum levels of citrulline and GvHD biomarkers and blood/stool measures of intestinal flora and function and allo-induced inflammation.

Central Committee Review

The COG SCT Discipline has created consensus guidelines for GvHD determination that are based on modified Glucksberg criteria. These guidelines have been used in COG transplant trials for the past decade. We will collect information that includes the highest grade of overall GvHD (grades 1-4) as well as the highest stages of organ GvHD (skin, GI and liver). For acute GI GvHD, we will collect both stage (1-4) for lower GI GvHD as well as presence (yes/no) of upper GI GvHD. Both upper and lower GI GvHD are used to determine the stage of GI GvHD, but lower GI GvHD alone will be considered an event. Dates of onset and maximal GI GvHD stage and overall grade will be collected. The Study Committee will audit the GvHD data (assuring that the reported stages correlate with overall grade) for each patient every 3 months. Additional information will be requested from the reporting center to review completed GvHD forms if the overall Grade of GvHD does not appropriately correspond to the reported stages. This targeted centralized review will identify cases most prone to error, will be more efficient than review of all data, and will avoid what otherwise would be an enormous hardship for centers. All reviewers will be blinded to the patient's regimen in order to limit any bias in determining the primary and exploratory endpoints. The study chair will make the final determination for GvHD

organ staging and overall grading based on central review and may override staging and grading entered by the institution.

9.3 Data Analytic Plan

Preliminary Descriptive Analysis: Study variables will be summarized using simple descriptive statistics such as count/percentage for categorical variables and mean/standard deviation/median/interquartile range for continuous variables. Baseline patient demographics and clinical characteristics will be summarized. The two arms will be balanced on the factors included in the stratified randomization. Treatment arms will be descriptively compared for other potential confounders for possible inclusion in the multivariate models. Arm comparison will be performed using simple two-sample tests, such as χ^2 test of proportions for categorical variables and independent t-tests or Wilcoxon rank sum tests for continuous variables. Analyses for each of the aims is presented below:

Primary Aim: The primary aim is to determine whether oral *LBP* prevents the development of Stage 1-4 GI aGvHD incidence in children and adolescents undergoing alloHCT. We hypothesize that administration of oral *LBP* will reduce the incidence of Stage 1-4 GI aGvHD compared to placebo. As described above, accrual will be conducted in two stages, the screening stage and the confirmatory stage. The proportion of 120 centrally reviewed, eligible and evaluable randomized patients who received at least 1 dose of treatment having Stage 1-4 GI aGvHD incidence from Day 0 through Day 120 will be compared between the two arms after the screening stage via two-sample unpooled chi-square test of proportions at 1-sided $\alpha=0.3$. If this liberal estimate of efficacy of *LBP* is demonstrated, accrual of the confirmatory stage will continue.

At the end of the confirmatory stage, the proportion of eligible patients having Stage 1-4 GI aGvHD incidence from Day 0 through Day 120 will be compared between the two arms (including patients randomized in both stages) via two-sample unpooled chi-square test of proportions at $\alpha=0.05$ (1-sided). We will use a modified intention-to-treat approach for the primary analysis.

Secondary analyses will be performed on cumulative incidence of Stage 1-4 GI aGvHD using unconditional multivariate logistic regression with covariate adjustment. Covariates, to be considered in the statistical models are: use of total body irradiation, duration of broad spectrum antibiotic usage, incidence of *C. difficile* infection, Haplo designation, and duration of total parenteral nutrition. We expect few patients to be terminated from aGvHD observation prior to Day 120 due to death, loss to follow-up, or consent withdrawal before determination of GI aGvHD outcome. Nevertheless, we will also perform secondary analyses (*time from graft infusion to first Stage 1-4 GI aGvHD onset*) via competing risk modeling, where graft failure, relapse and death are treated as competing events, generating incident curves and comparing treatment arms with the Gray's test to accommodate censoring. Patients without Stage 1-4 GI aGvHD will be censored when they meet criteria to be off study. Actuarial analyses will be extended for covariate adjustment using Cox proportional hazards regression. If we observe moderate protocol non-compliance with the daily *LBP*, additional analyses, such as as-treated analyses, subset analyses including only patients adherent with protocol treatment, or sensitivity analyses, will be performed to assess whether treatment adherence influenced the primary outcome. Based on our pilot results, we not anticipate a significant adherence problem.

Exploratory Aim 1: This aim is to determine whether administration of *LBP* prevents the development of moderate to severe (Grade II–IV) overall aGvHD. We hypothesize that

administration of *LBP* will reduce the incidence of Grade II–IV aGvHD in alloHCT recipients compared to placebo. We will use a similar analysis approached as described above for the primary aim but using the dichotomous cumulative incidence of Grade II–IV aGvHD as the endpoint measure.

Exploratory Aim 2: This exploratory aim is to determine whether *LBP* administration maintains intestinal integrity as measured by serum citrulline levels and reduces the incidence of mucosal barrier bloodstream infections (MBIs). We hypothesize that administration of *LBP* will maintain serum citrulline levels in alloHCT patients compared to patients receiving placebo. As well, we expect a lower incidence of MBIs in the *LBP* arm compared to placebo.

The citrulline levels at each of the time points will be summarized and described by arm. The mean quantitative change in citrulline level from start of conditioning to each of the four later time points will be compared between the 2 arms to determine if *LBP* administration maintains citrulline level via two-sample t-test and repeated-measures general linear modeling which include adjustments for potential confounders. In such analyses, multiple comparison adjustments for the 4 parallel analyses (linear contrasts) will be performed with Bonferroni adjustment to maintain an overall fixed α level. Linear mixed models, which include data from all time points for longitudinal data analyses with adjustment for within-patient correlation, will also be considered.

Likewise, we will compare the incidence of MBIs between two groups looking at the time from start of protocol treatment to first infection as the primary endpoint. Patients without infection will be censored when they meet criteria to be off study. Cox proportional hazards regression will be used to compare the incidence density of infection for the two groups adjusted for confounders (use of total body irradiation, duration of broad spectrum antibiotic usage, incidence of *C. difficile* infection, and duration of total parenteral nutrition). Main analyses for this aim will be based on a modified intention-to-treat principle (inevaluable patients will be excluded), but additional as-treated analysis, subset analysis, or sensitivity analysis may be performed if we observe issues with adherence to the randomized treatment on the study.

Exploratory Aims 3 and 4: These aims will examine the effects of *LBP* introduction on the intestinal flora of pediatric alloHCT recipients. The association between *LBP* administration and bacterial genes and pathways, and bacterial metabolites will be evaluated with Pearson's correlation coefficient with possible transformation to approximate normality. In addition to confirming the significance, a 95% confidence interval will be estimated for each marker. The total length of the interval depends on the observed correlation; the length will be 0.53 if the correlation is 0.40 and 0.24 if the correlation is 0.8. In addition to correlation, bivariate scatterplots will be used to display the association between *LBP* administration and each marker. Finally, we will perform a descriptive analysis examining the association between GvHD outcomes and bacterial genes, pathways, and metabolites using Cox regression. Additional regression models will adjust for other known GvHD risk factors.

Exploratory Aim 5: This aim will examine the effects of *LBP* on pro-inflammatory cytokines in alloHCT recipients. We hypothesize that *LBP*-associated maintenance or restoration in the microbiota will attenuate serum levels of pro-inflammatory cytokines in the early post-transplant period. We will use the same analytic approach as described for exploratory Aim 2 above.

Exploratory Aim 6: This aim will examine the effects of LBP on the incidence (yes/no) of *Clostridium difficile*-associated diarrhea in alternative donor HCT patients. Patients who have at least one incidence (positive) of *C. diff* during any reporting period is considered evaluable for this aim. We will compare proportion of *C. diff* during the study period between arms via the chi-square test.

Exploratory Aim 7: This aim will examine whether LBP administration reduces hospital days within the first 120 days post hematopoietic cell transplant. Total hospital days over the study period is calculated as the duration between the date of admission for conditional therapy and the date of discharge (or the study end date). Hospital days will be compared between arms by t-test (or Wilcoxon rank-sum test if assumptions for t-test are not met).

Exploratory Aim 8: This aim will examine the safety of orally administered LBP strains 299 and 299v in alternative donor HCT patients as measured by incidence (yes/no) of *Lactobacillus plantarum* bacteremia. Patients who have at least one incidence (positive) of *Lactobacillus plantarum* during any reporting period is considered evaluable for this aim. We will use the same analytic approach as described for exploratory Aim 6 above.

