1.2 Exploratory Aims

- 1.2.1 To determine whether orally-administered *LBP* decreases the incidence of Grade II–IV aGvHD following alternative donor alloHCT.
- 1.2.2 To determine whether *LBP* administration maintains intestinal integrity as measured by mean serum citrulline levels and reduction in mucosal barrier injury (MBI) bacteremia.
- 1.2.3 To measure the effects of *LBP* on the intestinal flora phylogenetic composition during and after alternative donor alloHCT using 16S rRNA gene deep sequencing.
- 1.2.4 To measure effects of *LBP* on intestinal flora function during and after alternative donor alloHCT using metagenomic and metabolite profiling.
- 1.2.5 To measure proposed immunomodulatory effects of *LBP* in mean serum levels of allereactive-induced inflammatory cytokines (IL-2, IL-6, IL-12p70, IFN γ , TNF α , etc.) in patients receiving *LBP* compared to placebo.
- 1.2.6 To determine whether *LBP* administration reduces the incidence of *Clostridium difficile*-associated diarrhea in alternative donor HCT patients.
- 1.2.7 To determine whether *LBP* administration reduces hospital days within the first 120 days post hematopoietic cell transplant (HCT).
- 1.2.8 To define the safety of orally administered *LBP* strains 299 and 299v in alternative donor HCT patients as measured by incidence of *Lactobacillus plantarum* bacteremia.

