Replenishing commensals like *Lactobacillus* prior to HCT in recipient mice substantially decreases aGvHD severity and intestinal insult.^{35,38} However, such attenuating effects of probiotic administration on aGvHD severity was limited to transplant recipients; as donor microbiota does not seem to influence alloreactive T-cell function and aGvHD course.³⁹ Dual effects of probiotics in maintaining intestinal cell function and inhibiting secretion of pro-inflammatory cytokines from intestinal mucosa suggest their beneficial role in the prevention and attenuation of aGvHD (Figure 1).^{35,38} Evidence from clinical studies further supports the hypothesis that altering the microbiota may affect clinical outcomes. For example, the provision of enteral feeding, in contrast to total parenteral nutrition, is associated with an increase in survival and reduced rates of aGvHD.^{40,41} Jenq et al also found that poor oral nutrition appears to more directly alter the composition of the microbiota compared to the conditioning regimen. It is hypothesized that administration of probiotic therapy will restore microbial diversity and maintain epithelial cell integrity, which together will preserve immune tolerance and prevent aGvHD. In addition, it is hypothesized that probiotic therapy will decrease susceptibility to enteric pathogens by maintaining intestinal luminal integrity.

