3.1.5 Randomization

Randomization will occur at the time of enrollment. Randomization will take place through the OPEN system. Upon enrollment, sites will receive notification of the kit number of study product that should be dispensed to the patient. All personnel at the site will remain blinded.

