4.3 Concomitant Therapy

4.3.1 Supplementation with any additional probiotic dietary supplements is not permitted (food containing live cultures like yogurt is allowed) through Day 120.

4.3.2 Prophylactic use of both broad-spectrum and narrow-spectrum antibiotics is permitted. Information regarding antimicrobial therapy (agent, start and stop times, indication for use) will be collected throughout the study time period.

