7.2 Data Collection

The following table represents data that will be collected during the study.

Studies	First day of conditioning [@]	Day 0 (Graft Infusion)	Day 7	Day 14	Day 28 or Discharge [%]	Day 56	Day 120
Review of LBP or placebo administration #	X	X	X	X	X	X	----
Use of TPN/EN (yes or no and days of administration)	X	X	X	X	X	X	X
Use of antimicrobial agents	X	X	X	X	X	X	X
Bloodstream infection	X	X	X	X	X	X	X
Clostridium difficile -associated diarrhea	X	X	X	X	X	X	X

[@]The first day of the transplant conditioning regimen is defined as the first day of chemotherapy or TBI, excluding any preceding anti T-lymphocyte antibody therapy. See [Section 4.2.1](#).

[%] Day 28 or day of discharge, whichever comes first.

[#] Total days product was administered will be collected for each reporting period. See [Section 4.2.2](#).

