
Skin and/or GI GVHD worsening
	
Liver GVHD is staged according to the Glucksberg criteria. The elevated bili is attributed to GVHD alone.
 
Thus, when skin or GI GVHD is worsening, there is no downgrading of liver GVHD staging for other causes of hyperbilirubinemia. (e.g., if TTP is diagnosed in the presence of stage 2 liver GVHD and worsening skin or GI GVHD, the liver is staged according to the actual bilirubin level even if some of the rise in bilirubin is attributed to TTP).
 
Similarly, even if there is no liver GVHD at onset of a new process, (such as TPN cholestasis), but skin or GI GVHD worsen during that process, then liver GVHD is diagnosed and staged according to the height of the bilirubin.
 
There is one exception to this: the diagnosis of TTP, with high LDH and unconjugated bilirubin precludes the diagnosis and staging of new liver GVHD in the absence of a confirmatory liver biopsy.

---	--

Table 3 Evaluating GI GVHD in the Absence of Biopsy Confirmation (See Table 4.0 below)

Establishing GI GVHD with new onset diarrhea and no skin or liver GVHD

No Skin/liver GVHD Day 0 through engraftment
	
Assume no GI GVHD, unless proven by biopsy
	

No Skin/liver GVHD Engraftment through day 100
	
NO other etiology of diarrhea identified: Stage as GI GVHD
	
Any other etiology of diarrhea identified: Do not stage as GI GVHD

Establishing GI GVHD with pre-existing diarrhea and skin or liver GVHD

Skin and/or liver GVHD present
	
Worsening diarrhea (includes worsening just prior to onset of skin or liver GVHD) OR persistent diarrhea despite resolution of non-GVHD cause: Stage as GI GVHD
	
Improving diarrhea after the diagnosis of skin or liver GVHD (irrespective of treatment) OR persistent diarrhea without resolution of underlying non-GVHD cause: Do not stage as GI GVHD

--	---	--

Differentiating Acute GVHD, Chronic GVHD, and Overlap Syndrome

There is often confusion differentiating acute from chronic GVHD, especially in the setting of reduced intensity transplants, DLI and new prophylactic treatments. The NIH Working Group recently published new classifications for GVHD:

Table 4 Acute GVHD, Chronic GVHD, and Overlap Syndrome

Category	Time of Symptoms after HCT or DLI	Presence of Acute GVHD features	Presence of Chronic GVHD features
Acute GVHD			
Classic acute GVHD	≤100 d	Yes	No
Persistent, recurrent, or late-onset acute GVHD	>100 d	Yes	No
Chronic GVHD			

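### The MBI Cox model and the secondary GI aGvHD models adjust the LBP effect for three variables that arise after randomization

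*Combined protocol and SAP*

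**What the plan says.** On timing, Section 3.1.5 states: "Randomization will occur at the time of enrollment". Section 3.1.4 places enrollment before the first dose and up to 14 days before conditioning.

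On the covariates, Section 9.3 has two lists.

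- **Secondary GI aGvHD models.** Logistic regression, with total body irradiation (TBI) and "duration of broad spectrum antibiotic usage, incidence of *C. difficile* infection, Haplo designation, and duration of total parenteral nutrition" as covariates to be considered. Adjustment is then extended to Cox regression, with no separate list.
- **MBI (Exploratory Aim 2).** A Cox model is to be used, "adjusted for confounders (use of total body irradiation, duration of broad spectrum antibiotic usage, incidence of *C. difficile* infection", and duration of parenteral nutrition). This wording is definite, and it is the only comparison of MBI between arms that the section specifies.

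On data collection, Section 4.3.2 says of antimicrobials: "Information regarding antimicrobial therapy (agent, start and stop times, indication for use) will be collected throughout the study time period". The table in Section 7.2 has "Use of TPN/EN (yes or no and days of administration") and C. difficile diarrhea, each from the first day of conditioning to Day 120. No pre-randomization version of the three variables is defined.

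Section 1.2.6 makes C. difficile an LBP outcome: to determine whether LBP "reduces the incidence of *Clostridium difficile*-associated diarrhea in alternative donor HCT patients".

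**The concern.** Randomization removes confounding by design, so a variable that arises afterwards is not a confounder of the arm comparison. Adjusting for it can do harm in two ways.

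1. **Mediation.** If LBP changes the covariate and the covariate affects the outcome, adjustment removes part of the LBP effect.
2. **Conditioning on a consequence.** If both LBP and the outcome change the covariate, adjustment creates an association that is not an effect of LBP.

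At stake is the meaning of the adjusted estimates. For MBI no unadjusted comparison is specified to set beside the adjusted one, so a real benefit could be understated or missed, or a null effect could look like harm. For GI aGvHD, a biased secondary estimate could appear to conflict with the primary test. Exploratory Aim 1 follows a similar approach to the primary aim and may inherit the same covariates.

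**Working it through.** The plan gives no figure on this point, so the check has two parts: the text, and the possible size.

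**Pathways in the text**

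- *C. difficile.* It is an outcome that LBP is meant to reduce (Section 1.2.6). It also enters the endpoint: Appendix III asks for infectious causes to be ruled out, and Table 3 says of post-engraftment diarrhea without skin or liver GvHD and without biopsy confirmation: "Any other etiology of diarrhea identified: Do not stage as GI GVHD". Toxin-positive diarrhea at entry is an exclusion (Section 3.3.6), so the covariate records later events.
- *Antibiotic days.* Section 2.3 hypothesizes that "probiotic therapy will decrease susceptibility to enteric pathogens by maintaining intestinal luminal integrity". An effect on antibiotic days is an inference from this, not a stated hypothesis. A bloodstream infection can itself lengthen antibiotic treatment.
- *Parenteral nutrition (TPN) days.* GI aGvHD can lengthen them. No passage says that LBP shortens them.

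Section 9.3 specifies no landmark or time-dependent coding, so a total duration would include days after the event.

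**Size, GI aGvHD logistic model**

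Inputs from the plan: 30% vs 18% and 227 per arm (Section 9.4), so the true OR = (0.18/0.82)/(0.30/0.70) = 0.512. Assumed: duration is normal with standard deviation SD, increased by g days if the event occurs and reduced by d days on LBP. Then

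log adjusted OR = log true OR + g·d/SD².

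With d = 2:

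| g | SD | g·d/SD² | Adjusted OR if true OR is 0.512 | Adjusted OR if true OR is 1.00 |
|---|---|---|---|---|
| 5 | 8 | 10/64 = 0.156 | 0.60 | 1.17 |
| 10 | 8 | 20/64 = 0.3125 | 0.70 | 1.37 |
| 10 | 10 | 20/100 = 0.20 | 0.63 | 1.22 |
| 10 | 12 | 20/144 = 0.139 | 0.59 | 1.15 |
| 10 | 15 | 20/225 = 0.089 | 0.56 | 1.09 |

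With d = 0 the added term is zero and the OR stays at 0.51.

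Power at one-sided 5%, SD 8 (4,000 simulated trials per case): 92% unadjusted. With d = 0 it is 90% (g = 5) or 84% (g = 10). With d = 2 it is 70% (g = 5) or 38% (g = 10).

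**Size, MBI Cox model (simulation)**

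All inputs except 227 per arm are assumed: constant hazard over 60 days, 20% MBI on placebo, total antibiotic days with mean 20, 10 more days if MBI occurs, entered as one fixed value.

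| True HR | SD | d | Adjusted HR | Power, one-sided 5% |
|---|---|---|---|---|
| 0.50 | 8 | 0 | 0.54 | about 79% (unadjusted about 89%) |
| 0.50 | 8 | 2 | about 0.70 | about 38–40% |
| 0.50 | 12 | 2 | about 0.58 | about 68% |
| 1.00 | 8 | 0 | 1.00 | – |
| 1.00 | 8 | 2 | about 1.25 | – |
| 1.00 | 12 | 2 | about 1.11 | – |

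At 30% MBI on placebo and SD 8, the 0.50 becomes 0.56 (d = 0) or about 0.69 (d = 2).

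**Size, C. difficile alone**

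Assumed: 20% on placebo, 10–12% on LBP, and an OR of 0.5 to 2 between C. difficile and recorded GI aGvHD. Holding the overall risks at 30% and 18% and solving for the adjusted OR gives 0.48 to 0.55, against 0.51.

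**The case against.** The strongest reply concerns size and reach.

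- **The large figures need an assumed effect.** The only LBP effect on these covariates that the plan states outright is on C. difficile, and there the distortion is small. If LBP does not change durations, the GI OR stays at 0.51 and the MBI HR moves only from 0.50 to 0.54. This stands.
- **The SD of 8 days is unsupported.** The distortion falls with the square of the SD, as the tables show. This stands, and is why a range is given.
- **The quoted powers are not those of planned tests.** The plan gives no alpha for MBI and no test for harm. This stands: the powers show loss of sensitivity only.
- **The 20% C. difficile rate is not a placebo rate.** It matches the pilot figure in Section 2.5, where patients received LBP. This stands; it is an assumption.
- **GI aGvHD has other unadjusted comparisons.** Besides the primary test, Section 9.3 plans Gray's test with incidence curves, and the GI covariates are only to be considered. This limits the harm for GI aGvHD but does not help MBI.
- **Antimicrobial start and stop times are collected, so pre-event coding is possible.** True, but the plan does not specify it, and it would not remove mediation.
- **There is a clinical reason to list TPN.** Section 2.3 links enteral feeding, in contrast to TPN, with less aGvHD. That makes nutrition prognostic, but it does not make its post-randomization duration a baseline variable.

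None of this answers the central point that the three variables arise after assignment.

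**Conclusion.** The concern holds. For MBI the plan is wrong as written: a definite model adjusts for post-randomization variables under the name of confounders. For GI aGvHD the list is tentative, and tightening it is a free improvement.

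Whether bias occurs, and how much, depends on effects that the documents do not give. With no LBP effect on durations it is nil for GI aGvHD and slight for MBI. With a 2-day effect and an event that adds 10 days, the adjusted GI OR is 0.56 to 0.70 for SD 15 down to 8, instead of 0.51, and the adjusted MBI HR is about 0.58 to 0.70 for SD 12 down to 8, instead of 0.50. In these duration examples the distortion works against LBP and does not create false efficacy; through C. difficile it can go either way. The screening decision and the primary test, both unadjusted, are not affected. This should be fixed before analysis, but it does not threaten the main conclusion of the trial.

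**What to change.** In every model that estimates the LBP effect on GI aGvHD or MBI, including any model for Exploratory Aim 1 that takes over the list, adjust only for pre-randomization variables: the Section 9.2 stratification factors (stem cell source including haplo, degree of HLA match, ATG/CAMPATH) and planned TBI. At present the MBI list has none of the stratification factors, and the GI list has only the haplo designation.

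Remove antibiotic duration, C. difficile infection and TPN duration from those models. Report the three by arm as outcomes, or use them in a separately labelled exploratory mediation analysis.

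The cost is SAP wording. The stratification factors are known at randomization. Section 9.3 refers to use of TBI and does not say when it is recorded, so planned TBI may need one enrollment field.
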